13.0 RECORDS TO BE KEPT / REGULATORY CONSIDERATIONS

Adverse event lists, guidelines, and instructions for AE reporting can be found in Section 8.0 (Adverse Events: List and Reporting Requirements).

13.1 Data Reporting

The OnCore Database will be utilized, as required by the Case Comprehensive Cancer Center, to provide data collection for accrual entry. OnCore is a Clinical Trials Management System housed on secure servers maintained at Case Western Reserve University. OnCore properly used is compliant with Title 21 CFR Part 11. Access to data through OnCore is restricted by user accounts and assigned roles.

Data will be entered into the Cancer Center Clinical Trials Oncore Database. The Investigator will ensure that the records and documents pertaining to the conduct of the study and the distribution of the protocol therapy, that is copies of CRFs and source documents (original documents, data, and records [e.g., hospital records; clinical and office charts; laboratory notes; SAE reports]) be retained by the Investigator for as long as needed to comply with national and international regulations (generally 2 years after discontinuing

clinical development). The records of this study will be kept private. Information that may be gained from this study will be used for research and educational purposes only. In any report that might get published, no information will be included that would allow for identification of the patient. At any time the Investigator may be subject to a field audit by regulatory authorities (e.g., FDA, TPP, EMEA) in order to validate the participation of subjects in the study. Therefore, careful attention should be paid to seeing that all study documents/records are complete, accurate, and filed and retained by the Investigator.

13.2 Regulatory Considerations

The study will be conducted in compliance with ICH guidelines and with all applicable federal (including 21 CFR parts 56 & 50), state or local laws.

13.2.1 Written Informed Consent

Provision of written informed consent must be obtained prior to any study-related procedures. The Principal Investigator will ensure that the subject is given full and adequate oral and written information about the nature, purpose, possible risks and benefits of the study as well as the subject's financial responsibility. Subjects must also be notified that they are free to discontinue from the study at any time. The subject should be given the opportunity to ask questions and allowed time to consider the information provided.

The original, signed written Informed Consent Form must be kept with the Research Chart in conformance with the institution's standard operating procedures. A copy of the signed written Informed Consent Form must be given to the subject.

13.2.2 Subject Data Protection

In accordance with the Health Information Portability and Accountability Act (HIPAA), a subject must sign an authorization to release medical information to the sponsor and/or allow the sponsor, a regulatory authority, or Institutional Review Board access to subject's medical information that includes all hospital records relevant to the study, including subjects' medical history.

13.2.3 Retention of Records

The Principal Investigator of The Cleveland Clinic supervises the retention of all documentation of adverse events, records of study drug receipt and dispensation, and all IRB correspondence for as long as needed to comply with national and international regulations. No records will be destroyed until the Principal Investigator confirms destruction is permitted.

13.2.4 Audits and Inspections

Authorized representatives of the sponsor, a regulatory authority, an Independent Ethics Committee (IEC) or an Institutional Review Board (IRB) may visit the Center to perform audits or inspections, including source data verification. The purpose of an audit or inspection is to systematically and independently examine all study-related activities and documents to determine whether these activities were conducted, and data were recorded, analysed, and

accurately reported according to the protocol, Good Clinical Practice (GCP), guidelines of the International Conference on Harmonization (ICH), and any applicable regulatory requirements.

13.2.5 Data Safety and Monitoring Plan

This protocol will adhere to the policies of the Case Comprehensive Cancer Center Data and Safety Monitoring Plan in accordance with NCI regulations.

14.0 STATISTICAL CONSIDERATIONS

Considering the potential for missed doses of methotrexate or other drug, this investigation will be based on an intent to treat analysis. This study hopes to show a reduction in the incidence of severe mucositis and time to neutrophil and platelet engraftment while not increasing the incidence or severity of acute GVHD in the allogeneic HCT population.

Our current rate of severe (grade 3-4) mucositis is 41%. Ninety-four (47 in each group) would be needed to demonstrate a 25% improvement in mucositis to 16%, based on a one-sided test with 5% significance and 80% power.

Our current estimate of mean day to neutrophil engraftment is 19 days. One hundred patients (50 in each group) would be needed to demonstrate a 4 day improvement in time to neutrophil engraftment based on a one-sided test with 5% significance and 80% power.

Our current percent of patients achieving platelet engraftment by day 21 is 26%. Ninety-eight (49 in each group) would be needed to demonstrate a 25% improvement in platelet engraftment to 51%, based on a one-sided test with 5% significance and 80% power.

Our current rate of any acute GVHD by day 60 is 62%. If the hazard ratio between treatment arms is at most 1.7, then we will conclude that the new treatment does not significantly increase acute GVHD. Forty-five patients per group are needed to detect this hazard ratio using a one-sided non-inferiority log-rank test with 5% significance and 80% power.

Therefore, this study requires 100 patients to have a minimum of 80% power to address all of the primary objectives.

Overall survival and progression-free survival will be estimated using the Kaplan-Meier method and compared between patients receiving Tac and MTX versus Tac, mini-MTX, and MMF using the log-rank test. Hospital stay will be compared between groups using the Wilcoxon rank sum test. TPN and 100-day incidence of complications will be compared using the Chi-square test. Acute and chronic GVHD will be estimated using cumulative incidence methods and compared using the Pepe-Mori test.

REFERENCES

1. Horan JT et al. Reducing the Risk for Transplantation-Related Mortality after Allogeneic Hematopoietic Cell Transplantation: How Much Progress Has Been Made? *JCO* 2011; 29: 805-813
2. Weisdorf D et al. Treatment of moderate/severe acute graft-versus-host disease after allogeneic bone marrow transplantation: an analysis of clinical risk features and outcome. *Blood* 1990; 75: 1024-1030

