APPENDIX IV

TBI Administration

1.0 **INTRODUCTION**

1.1 **Allogeneic Hematopoietic Cell Transplant**

Allogeneic hematopoietic cell transplantation (HCT) is an effective therapy for a variety of hematologic malignancies and bone marrow failure syndromes. However, it carries a significant risk for treatment-related mortality, primarily due to infection, conditioning regimen-related toxicities, and graft versus host disease (GVHD); which continues to limit its utility. The risk of transplant-related mortality (TRM) is influenced by several factors, including patient age, disease remission status, number of prior chemotherapy regimens, co-morbid diseases, and conditioning regimen intensity. Since the 1980's, several advances have reduced the risk of TRM in patients undergoing allogeneic HCT; including more effective approaches for prevention of infection, enhancements in HLA typing and matching, and GVHD prophylactic regimens [1]. Despite this however, TRM remains high and GVHD remains a major cause of morbidity and mortality amongst allogeneic HCT patients. Even with prophylactic measures, the incidence of acute GVHD is estimated to be 40-50% among patients from HLA identical sibling donors and up to 75% in patients receiving unrelated transplants. Treatment for established GVHD can be difficult, with a mortality rate of 60-80% in patients with grades 3-4 acute GVHD. Approximately 40% of patients with acute GVHD have a durable response to corticosteroid therapy, and there has been little change in this response rate over the past 20 years despite changes to GVHD treatment regimens [2]. Thus the use of improved and effective prophylaxis is of utmost importance.

1.2 **GVHD Prophylaxis**

Currently, GVHD prophylaxis is based on a calcineurin inhibitors (cyclosporine (CsA) or tacrolimus (Tac) also called FK-506) and a short course of methotrexate (MTX). Other options include steroids, mycophenolate mofetil (MMF), and sirolimus. While the combination of Tac and MTX has largely been shown to be superior in the prevention of aGVHD compared to other regimens, toxicities from these regimens are a cause of significant morbidity after allogeneic transplant.

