2.2 Secondary Objectives

- Length of hospitalization/time to discharge
- Use of TPN (total parenteral nutrition)
- Length of time on continuous infusion narcotics
- Incidence of infection in the first 100 days post-transplantation
- Incidence of hepatotoxicity in first 100 days post-transplantation
- Incidence of nephrotoxicity in first 100 days post-transplantation
- Incidence of pulmonary toxicity in first 180 days post-transplantation
- Incidence and severity of grade II-IV and III-IV acute GVHD
- Incidence and severity of chronic GVHD
- One year relapse-free and overall survival

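### Acute GVHD non-inferiority: 100 patients give about 67% power (day 60) to 77% (day 100, constant hazard assumed), not the stated minimum of 80%; the named analysis test has no margin

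*Combined protocol and SAP*

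**What the plan says.** Section 2.1 makes the incidence of acute GVHD a primary objective, with no grade limit and no time window. Section 14.0 gives the planning rate: "Our current rate of any acute GVHD by day 60 is 62" per cent. It then states the conclusion rule, "If the hazard ratio between treatment arms is at most 1.7, then we will conclude that the new treatment does not significantly increase" acute GVHD, and the size: "Forty-five patients per group are needed to detect this hazard ratio", "using a one-sided non-inferiority log-rank test with 5% significance and 80% power". After sizing the other primary endpoints it concludes that "this study requires 100 patients to have a minimum of 80% power to address all of the primary objectives".

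The analysis paragraph at the end of Section 14.0 does not mention the non-inferiority test again. Its only sentence on this endpoint is: "Acute and chronic GVHD will be estimated using cumulative incidence methods and compared using the Pepe-Mori test".

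Three other places matter:

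- Section 1.1 puts acute GVHD incidence despite prophylaxis at "40-50% among patients from HLA identical sibling donors and up to 75% in patients receiving unrelated transplants", without grade or window.
- Section 2.2 lists "Incidence and severity of grade II-IV and III-IV acute GVHD" as secondary. Section 12.3, however, measures acute GVHD by those same grades, next to mucositis (12.1) and engraftment (12.2), and the secondary list in 12.4 leaves acute GVHD out.
- Section 11.1.5 has acute GVHD documented to day +100.

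**The concern.** The power of a log-rank test depends on the number of events, not the number of patients. A requirement of 45 patients per group sits oddly beside a 62% event rate, because it leaves only about 56 events for a margin of 1.7.

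This objective is the trial's check that cutting the methotrexate dose does not cost GVHD control. If its power is overstated, a regimen that is truly no worse may fail to show non-inferiority more often than readers were told, and the failure may be misread as evidence of harm.

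The analysis wording adds a second risk. The conclusion rule does not say whether the estimate or its upper limit must be at most 1.7. The test named for the analysis looks for a difference, and a non-significant difference test in a trial of this size is not evidence of non-inferiority.

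**Working it through.** **Inputs.** Margin 1.7, one-sided 5%, 80% power, 45 per group, 62% by day 60 (Section 14.0); 1:1 allocation (5.1); 50 per group (3.2). Assumed: true hazard ratio 1, since the plan states no alternative.

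**Events needed (Schoenfeld).** 4 × (1.645 + 0.842)² / (ln 1.7)² = 4 × 6.183 / 0.2816 = 87.8, or 88 events. Freedman's formula gives 92. Two-sided versions need 112 and 117.

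**Trying to reproduce 45 per group.** Patients per group = events / (2 × event proportion).

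| Event proportion | Schoenfeld | Freedman |
|---|---|---|
| 62% (as stated) | 71 | 75 |
| 71.3% (mean of 62% and the 80.7% implied by a hazard ratio of 1.7) | 62 | 65 |
| 80.1% (constant hazard to day 100) | 55 | 58 |
| 94.5% (constant hazard to day 180) | 47 | 49 |
| 99.7% (constant hazard to day 365) | 45 | 47 |
| 100% | 44 | 46 |

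The figure of 45 comes back only when nearly every patient has an event. It lies close to the number of events needed per group, which would fit events having been taken as patients, but the documents do not show the derivation.

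**Proportion that must have an event.** 87.8 / 90 = 97.6% for the plan's 45 per group; 87.8 / 100 = 87.8% for the full trial. The highest acute GVHD figure in the documents is the upper value of 75% for unrelated donors.

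**Power.** Φ(ln 1.7 × √d / 2 − 1.645), where d is the number of events.

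| Setting | d | Power |
|---|---|---|
| 90 patients, 62% | 55.8 | 63.2% |
| 100 patients, 62% (day 60) | 62 | 67.2% |
| 100 patients, day 100 | 80 | 76.7% |
| 100 patients, 40% (Section 1.1) | 40 | 51% |
| 100 patients, 50% (Section 1.1) | 50 | 59% |
| 100 patients, 75% (Section 1.1) | 75 | 74% |

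The day-100 row assumes that the day-60 hazard continues: 1 − 0.38^(100/60) = 80.1%. The documents give no day-100 rate. Simulation with 50 per group, 5,000 trials and a Cox upper limit agrees: 66.0% at day 60 and 75.5% at day 100.

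**If grade II-IV is the primary endpoint.** Those events are a subset of any-grade events over the same window, so at a true hazard ratio of 1 power can be no higher.

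**What the named test demands.** With 62 events, the upper limit is below 1.7 only if the observed hazard ratio is below exp(ln 1.7 − 2 × 1.645 / √62) = 1.12. With 80 events the bound is 1.18. A rule on the point estimate alone would pass 50% of the time at a true hazard ratio of 1.7, against 5% for the test.

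**The case against.** **The window may be longer.** Day 60 appears only as the time point of a historical rate, and monitoring runs to day +100. This stands: 67% should not be given as the single answer. At day 100 the shortfall is about 3 points rather than 13, under an assumed constant hazard. Power passes 80% only if that hazard is carried to day 180 (82.5%) or day 365 (84.2%), beyond the day +100 monitoring window.

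**The true hazard ratio may be below 1.** At 0.95, power is about 74% (day 60) or 83% (day 100). With 62 events, 80% power needs a true ratio of about 0.90. The plan states no such benefit; its aim is only that acute GVHD should not increase. Any power statement must nonetheless carry its assumed ratio.

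**The decision rule is not as loose as it reads.** A reader might infer that non-inferiority will be declared on the point estimate. The documents do not support that. The next sentence names a one-sided 5% non-inferiority log-rank test, which implies an upper limit below 1.7. The missing bound is an ambiguity to close, not proof that the trial lacks an inferential criterion.

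**The endpoint hierarchy is unsettled.** A reader might infer from Section 2.2 that graded acute GVHD is purely secondary, that any grade by day 60 is primary, and that Pepe-Mori was meant for the grades only. Sections 12.3 and 12.4 point the other way, so the documents do not settle it.

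**Conclusion.** The sizing statement is wrong as written. On the plan's own margin, error rate and event rate, 45 per group does not give 80% power, and 100 patients do not give the promised minimum. Power is about 67% at day 60 and about 77% at day 100, so a truly equal regimen would fail to show non-inferiority roughly one time in three to one in four. This rests on a true hazard ratio of 1, on the 62% rate and, for day 100, on a constant hazard. Deaths before GVHD would lower the event count; the documents give no rate, so none was applied.

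The analysis text is a smaller problem but a real one. The only test named for analysing acute GVHD has no margin and cannot deliver the non-inferiority conclusion, while the test that can appears only in the sizing. Which grade and window define the primary endpoint remains open in the documents.

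**What to change.** 1. In Section 14.0, restate power for this objective as about 67% (events to day 60) to 77% (to day 100, constant hazard assumed), with 100 patients and a true hazard ratio of 1. Remove the claim of at least 80% for this objective.
2. Reconcile Sections 2.1, 2.2, 12.3 and 14.0 on whether the primary acute GVHD endpoint is any grade or grade II-IV/III-IV. State the window: day 60, or day 100 as monitored in 11.1.5. If a graded endpoint is chosen, restate power from its own rate.
3. State that non-inferiority on that endpoint is concluded only if the one-sided 95% upper confidence limit of the hazard ratio (Group B versus Group A) is below 1.7, in the intent-to-treat population.
4. Use Pepe-Mori only for the remaining acute and chronic GVHD comparisons, and say that a non-significant result is not to be read as non-inferiority.

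The cost is a few sentences, with no added patients or data. The stated power becomes less favourable, but that shortfall already exists in the sizing. For reference only, 80% power would need about 142 patients at a 62% event rate (87.8 / 0.62 = 141.6).

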1.3 Clinical Data to Date

The group at M.D. Anderson Cancer Center has developed a mini-dose methotrexate regimen (5 mg/m² IV on days 1, 3, 6, and 11) in an effort to reduce mucosal and hepatic complications and have published small studies on its use in combination with both CsA and Tac [10-11]. These studies have demonstrated the safety and efficacy of this regimen in HLA matched and 1 antigen mismatched unrelated donors, with an incidence of grade 2-4 acute GVHD of 33-59% and grade 3-4 acute GVHD of 17%. Tac and mini-dose MTX (5mg/m² IV on days 1, 3, and 6 only) has been further tested in combination with a third agent [12-13]. Mizumoto et al used a combination of Tac, mini-dose MTX and MMF as GVHD prophylaxis in reduced-intensity transplants and demonstrated a safe and well tolerated profile with a low incidence of severe grade 3-4 GVHD (5%). While these studies have demonstrated the safety and efficacy of these regimens, there have been no studies directly comparing mini-dose MTX and standard dose MTX based GVHD prophylactic regimens.

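### The hazard-ratio-1.7 rule for acute GVHD does not say whether the estimate or its bound must meet 1.7, its planned conclusion claims more than a pass would show, and severity has no margin

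*Combined protocol and SAP*

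**What the plan says.** All of this is in Section 14.0 unless stated otherwise.

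- **Aim.** The study hopes to reduce severe mucositis and time to engraftment "while not increasing the incidence or severity of acute GVHD".
- **Control rate.** "Our current rate of any acute GVHD by day 60 is 62" per cent.
- **Rule.** If the hazard ratio is no more than 1.7, "then we will conclude that the new treatment does not significantly increase acute GVHD".
- **Size.** "Forty-five patients per group are needed to detect this hazard ratio" "using a one-sided non-inferiority log-rank test with 5% significance and 80% power".
- **Analysis.** The closing paragraph says that acute and chronic GVHD will be estimated by cumulative incidence and compared with the Pepe-Mori test. It mentions no hazard ratio, confidence bound or margin for GVHD.

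The plan gives no reason for 1.7 and does not translate it into an incidence. Section 2.1 makes the incidence of acute GVHD a primary objective. Section 2.2 lists grade II-IV and III-IV disease as secondary. Section 12.3 lists both for comparison, without a margin.

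**The concern.** The rule has three gaps.

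1. The planned conclusion uses the language of a difference test, but the margin belongs to a non-inferiority test. Passing a non-inferiority test shows that an increase as large as the margin has been excluded. It does not show that there is no significant increase.
2. The rule refers to the hazard ratio without saying whether the estimate or its upper confidence bound must meet 1.7. The two readings give very different trials. The analysis paragraph does not settle it, because the test named there has no margin.
3. The aim covers severity, but the only margin is for acute GVHD of any grade. Under Appendix I that endpoint includes grade I skin disease, so a shift from mild to severe disease could leave it unchanged.

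The GVHD result is the safety counterweight to the hoped-for gains in mucositis and engraftment. How it is worded decides how a positive trial would be read.

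**Working it through.** **Inputs.** Section 14.0 gives the control rate of 62% by day 60, the margin of 1.7, one-sided 5% and 80% power. Section 3.2 gives 50 patients per group. Section 1.3 gives the grade 3-4 rates of 17% and 5%.

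**The plan's own figure.** Schoenfeld events for a margin of 1.7 are 4 × (1.645 + 0.842)² / (ln 1.7)² = 88. The 45 per group is reached only if almost every patient has an event, since 88 / 2 = 44. At 62% it would be 88 / 0.62 = 142 patients, or 71 per group. So 45 per group does not follow from the 62% rate. That is a separate matter, but it means the calculations below should use the expected event count. With 50 per group and 62% in both arms, this is 100 × 0.62 = 62 events.

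**What the margin means as an incidence.** Under proportional hazards and with no deaths before GVHD, the rate in Group B is 1 − (1 − control rate)^1.7.

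| Control rate by day 60 | Rate at hazard ratio 1.7 | Rise |
|---|---|---|
| 62% (plan) | 1 − 0.38^1.7 = 80.7% | 18.7 points |
| 50% (illustrative) | 1 − 0.50^1.7 = 69.2% | 19.2 points |
| 40% (illustrative) | 1 − 0.60^1.7 = 58.0% | 18.0 points |

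**The two readings of the rule.** The standard error of the log hazard ratio is about 2 / √events.

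- *Significant increase, one-sided 5%:* observed ratio above exp(1.645 × 2 / √events).
- *Upper one-sided 95% bound below 1.7:* observed ratio below 1.7 × exp(−1.645 × 2 / √events).

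| Events | Significant increase above | Bound meets 1.7 below |
|---|---|---|
| 62 (62% in both arms) | 1.52 | 1.12 |
| 71 (62% and 80.7%: 50 × 0.62 + 50 × 0.807) | 1.48 | 1.15 |

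With 62 events:

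- *Point-estimate reading.* An observed ratio from about 1.52 to 1.7 passes. At 1.7, z = ln 1.7 × √62 / 2 = 2.09, one-sided p about 0.02. A statistically significant increase would be reported as not significant. In day-60 terms this band runs from 1 − 0.38^1.52 = 77% to 81%, against 62%. If the true ratio is 1.7, the trial passes half the time.
- *Bound reading.* The observed ratio must be about 1.12 or lower, or 1 − 0.38^1.12 = 66% by day 60. If the true ratio is 1.7, the trial passes 5% of the time, by construction.

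**Severity.** With 50 per arm and the same rate p in both arms, the one-sided 95% bound on the difference is 1.645 × √(2p(1 − p) / 50).

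- p = 5%: 1.645 × 0.0436 = +7 points.
- p = 17%: 1.645 × 0.0751 = +12 points.

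Both rates are illustrative. The 17% ("grade 3-4 acute GVHD of 17" per cent) comes from a four-dose mini-methotrexate regimen in matched and one-antigen-mismatched unrelated donors. The 5% comes from tacrolimus, mini-dose methotrexate and MMF after reduced-intensity conditioning. Neither is the population of this trial.

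**The case against.** The strongest reply is that Section 14.0 names a non-inferiority test, and such a test is ordinarily passed on the confidence bound. On that reading the trial is strict: an observed day-60 rate much above 66% against 62% would fail. Anyone who inferred that a true 81% would readily pass would be wrong under the named test. This stands, and it limits the concern. It does not remove it, because the test appears only in the sample-size sentence, the rule itself does not mention a bound, and the analysis paragraph names a different test.

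A second reply is that the choice of margin is a judgement. That also stands, and nothing here asks for a different margin. A reader might go further and say that 81% is unacceptable because it exceeds the Section 1.1 figure of "up to 75% in patients receiving unrelated transplants". The documents do not support using that figure as a ceiling. It has no time point or grade, and it concerns unrelated transplants. The 62% is the centre's own day-60 rate, and Section 4.1 admits both related and unrelated 8/8 matches.

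A third reply is that the protocol makes no decision on severity. Non-increase in severity is stated as a hope, graded disease is secondary in Section 2.2, and a secondary endpoint needs no margin. This is right: a reader might infer a planned severity conclusion, but there is none. What remains is narrower. The aim puts severity beside incidence as something not increased, and the design offers no way to show it.

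**Conclusion.** The concern holds in a limited form. As written, the rule allows a conclusion that the margin does not support. A pass excludes a hazard ratio of 1.7 or more, which is about 81% by day 60 when the control rate is 62%, a rise of about 19 points. On the point-estimate reading, which the text leaves open, an observed ratio from about 1.52 to 1.7 with 62 events would contradict the conclusion that the plan attaches to it. On the bound reading, the test is sound and only the wording claims too much.

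The 81% assumes proportional hazards and no deaths before GVHD. The documents give no early death rate from which to adjust it. The thresholds depend on the event count and move only slightly between 62 and 71 events.

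For grade III-IV disease, 50 per arm and no margin cannot support a statement of no increase: the bound is about +7 to +12 points over the illustrative rates. This does not mean that severe GVHD is expected to rise by that amount, or that 17% is the rate to expect here.

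**What to change.** In Section 14.0:

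1. Keep the margin of 1.7. State that non-inferiority is met only if the one-sided 95% upper bound of the hazard ratio is below 1.7.
2. Replace the planned conclusion with a statement that a pass excludes a hazard ratio of 1.7 or more, equivalent to about 81% by day 60 if the control rate is 62%, under proportional hazards.
3. In the analysis paragraph, name the hazard-ratio analysis that yields this bound, so that Pepe-Mori is not the only comparison specified for acute GVHD. Report the day-60 cumulative incidence difference with its one-sided 95% bound.
4. Remove severity from the non-increase aim. Report the grade III-IV difference with its confidence interval as descriptive.

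The cost is a few sentences and one added estimate. No patients are added, and treatment and the margin stay as they are. The downside is that the permitted claim is less favourable. The fix also makes visible that, with 62 events, the chance of passing when the arms are truly equal is Φ(2.09 − 1.645), about 67%. That follows from the event count under the test already named, not from the rewording.

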3.2 Number of Subjects

We plan to enroll 50 subjects in each group for a total of 100 subjects.

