5.1 Randomization

Patients will be randomized 1:1 to one of the two GVHD prophylaxis regimens using blocked randomization with random block sizes. The randomization list will be generated before the start of the study by the study statistician of the study using a SAS randomization program; the list will be kept in a secured location which will only be accessible to the study coordinator. Randomization will be stratified by TBI in the preparative regimen (yes, no), donor relationship (related, unrelated), and source of hematopoietic cells (PBSC, marrow).

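### The acute GVHD non-inferiority sample size works only if nearly every patient has an event; at the plan's own 62% rate, power is about 63% with 45 per group and 67% with 50, not 80%

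*Combined protocol and SAP*

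**What the plan says.** Section 14.0 sizes each primary objective in turn. For acute GVHD it gives a baseline, "Our current rate of any acute GVHD by day 60 is 62" per cent, and a decision rule: "If the hazard ratio between treatment arms is at most 1.7, then we will conclude that the new treatment does not significantly increase acute GVHD". It then states: "Forty-five patients per group are needed to detect this hazard ratio using a one-sided non-inferiority log-rank test", at the 5% level with 80% power. It gives no number of events, no assumed true hazard ratio and no event probability other than the day-60 figure.

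The section concludes that "this study requires 100 patients to have a minimum of 80% power to address all of the primary objectives". Section 3.2 fixes enrolment ("We plan to enroll 50 subjects in each group for a total of 100 subjects") and Section 5.1 the allocation ("Patients will be randomized 1:1 to one of the two GVHD prophylaxis regimens"). Section 3.3 replaces patients who drop out before the day-100 endpoints can be evaluated, so no inflation for drop-out applies. Section 11.1.5 has acute GVHD monitored and documented until day +100.

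**The concern.** The information in a log-rank test comes from events. Where 62% of patients have an event, the number of patients must be well above the number of events required. Here the two nearly coincide: about 88 events are needed and 90 patients are stated. The 62% rate seems to have had almost no effect on the result.

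Acute GVHD is the safety half of the trial's claim. Section 14.0 hopes for less severe mucositis and faster engraftment without more acute GVHD, and the experimental arm reduces methotrexate. If power is overstated, the trial will fail to show non-inferiority between truly equal regimens more often than readers are told. They cannot see this for themselves, because no event count is given. The sentence that justifies the total of 100 patients would also be untrue for this objective.

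**Working it through.** **Inputs.** From Section 14.0: margin HR 1.7, one-sided alpha 0.05 (z = 1.645), power 80% (z = 0.842), 62% with any acute GVHD by day 60, 45 per group. From Sections 3.2 and 5.1: 50 per group, 1:1. Assumed, because the plan does not state it: true HR 1.0, the usual choice for non-inferiority and consistent with the aim of not increasing acute GVHD.

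**Step 1: events required.**
- Schoenfeld: D = 4(1.645 + 0.842)² / (ln 1.7)² = 87.8, so 88 events.
- Freedman: D = (1.645 + 0.842)² × [(1 + 1.7)/(1.7 − 1)]² = 92.0 events.

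**Step 2: reproduce the plan's 45 per group.**
- If every patient is an event, 87.8/2 = 43.9 gives 44 per group (Schoenfeld) and 92.0/2 gives 46 (Freedman).
- With a constant hazard fitted to the plan's rate, λ = −ln(0.38)/60 per day. Run to day 365, this gives 1 − exp(−365λ) = 99.7% events, and 87.8/(2 × 0.997) = 44.04, rounded up to 45. This matches exactly, but it requires almost every patient to develop acute GVHD within a year.
- Using the 62% rate as stated, 87.8/0.62 = 141.7 patients, or 71 per group (75 with Freedman).
- Binary comparisons based on 62% give 72 to 89 per group.

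**Step 3: power at the stated sizes.** Power = Φ(ln(1.7) × √D / 2 − 1.645).

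| Event proportion | Events / power, 90 patients | Events / power, 100 patients | Per group for 80% (Schoenfeld) |
|---|---|---|---|
| 62% (plan, day 60) | 55.8 / 63.2% | 62.0 / 67.2% | 71 |
| 71.3% (mean of 62% and 80.7%, the new arm's rate at HR 1.7) | 64.2 / 68.5% | 71.3 / 72.5% | 62 |
| 75% (highest background rate in Section 1.1) | 67.5 / 70.4% | 75.0 / 74.3% | 59 |
| 80.1% (constant hazard to day 100) | 72.1 / 72.8% | 80.1 / 76.7% | 55 |
| 100% | 90.0 / 80.8% | 100.0 / 84.3% | 44 |

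For the first row with 100 patients: 0.5306 × √62 / 2 − 1.645 = 0.444, and Φ(0.444) = 0.672.

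**Step 4: simulation check.** Exponential times, censoring at day 60, true HR 1.0 and a score test of HR = 1.7 gave power of 64.3% with 45 per group, 68.1% with 50 and 80.4% with 71 (20,000 runs each). The formula is not misleading at these sizes.

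**Step 5: what 80% power would require.** The event proportion would have to be 87.8/90 = 98% with 90 patients or 87.8/100 = 88% with 100. With 62 events, the margin that 80% power supports is exp(2 × 2.487/√62) = 1.88, not 1.7.

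**The case against.** Four points can be made for the plan.

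- **The cause is not proven.** Taking patients as events gives 44 or 46, not 45, whereas extending the day-60 hazard to the one-year follow-up of Section 3.4.2 gives exactly 45. The author may therefore have used the 62% correctly with too long a horizon. This stands as to cause: the documents do not show how 45 was reached. It does not rescue the figure. Both routes make nearly everyone an event, and the second runs far past the end of acute GVHD monitoring.
- **Day 60 is not declared as the analysis cut-off.** Section 14.0 gives it as the horizon of the historical rate, while the documented window is day +100. This also stands, and 67% is therefore the lower end of a range for 100 patients. The upper end, about 77%, assumes that the hazard stays constant after day 60. If onset slows, the true figure is lower. Neither end reaches 80%.
- **The trial enrols 50 per group, not 45.** That is so, and 67% is the figure that matters for the trial as planned. The 63% tests the plan's own claim for 45.
- **A true hazard ratio below 1 would restore power.** At day 60, 80% is reached if the true HR is about 0.86 with 90 patients or 0.89 with 100. The plan states no such expectation for acute GVHD. Its aim is no increase.

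Separately, the closing paragraph of Section 14.0 plans to compare acute GVHD with the Pepe-Mori test, which is not the non-inferiority log-rank test used for sizing. That mismatch needs its own resolution and does not restore the stated power.

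**Conclusion.** The stated sample size and power are wrong as written. With the plan's margin, significance level and 62% event rate, and a true HR of 1.0, 45 per group gives about 63% power and the planned 50 per group about 67%. Counting events to day 100 under a constant hazard raises the latter to at most about 77%. The claim of at least 80% power for all primary objectives therefore fails for acute GVHD.

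If the regimens are equal, the trial would miss non-inferiority about one time in three at day 60 (1 − 0.672 = 0.328), or a little under one in four at day 100 (1 − 0.767 = 0.233), against the one in five implied.

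These figures assume proportional hazards, equal event rates in both arms, and a decision based on the one-sided 95% upper confidence limit lying below 1.7. Death or relapse before acute GVHD, if treated as ending follow-up for it, would reduce events and power further. How the author arrived at 45 is inference; the shortfall is not.

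**What to change.** Restate the acute GVHD paragraph in Section 14.0 to say that:

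- about 88 events are needed for 80% power against a margin of 1.7 (one-sided 5%, true HR 1.0);
- 50 per group is expected to give about 62 events by day 60 and about 67% power;
- if events are counted to day 100, power is at most about 77%, assuming a constant hazard.

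State which horizon the analysis uses. Day 100 is the better choice for power and needs no new assessments, since the protocol already monitors to that point. Remove the sentence claiming at least 80% power for all primary objectives, or limit it to the objectives for which it holds. Name the test to which the power figure refers, so that it agrees with the planned acute GVHD comparison.

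The cost is a revision of wording and a less favourable stated power. Enrolment and procedures do not change. If the sponsor wants to keep 80% power against 1.7, about 71 per group would be needed at day 60, or 55 per group at day 100 under the constant-hazard assumption. Widening the margin to the 1.88 that 62 events would support should not be done merely to recover the power figure.
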